3.2 Study Aims

The primary aim is the need for intravenous or immediate-release oral therapy for acute treatment of severe hypertension.

3.3 Secondary Aims

The secondary aims of this study are to evaluate

- Route of delivery
- Indications for cesarean section (uncontrolled hypertension, failure to progress, non-reassuring fetal well-being, etc)
- Maternal hypotension (<30% baseline or mean arterial pressure $<$ 65 mmHg)

- Time from enrollment to hospital discharge
- Postpartum hypertension control, including frequency and dosing of acute or maintenance antihypertensive therapy
- Composite of adverse maternal outcomes (time duration to need for acute antihypertensive therapy, receipt of second dose study drug, time from randomization to delivery, seizure, adverse CNS outcome (stroke or cortical blindness), pulmonary edema, oliguria, DIC, admission to ICU, dialysis, mechanical ventilation, abruption, post-partum hemorrhage, receipt of blood products, maternal death)
- Composite of adverse neonatal outcomes (intrapartum fetal demise, abruption, neonatal death, Apgar score <7 at 5 minutes, intubation, convulsions, IVH, confirmed sepsis, RDS requiring O2, NICU admission)

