1.4 Secondary Aims

The secondary aims of this study are to assess the effect of Nifedipine 30mg XL compared with placebo on mode of delivery, indications for cesarean delivery, maternal hypotension and other adverse events, and a composite of maternal and perinatal adverse outcomes.

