Acute blood pressure treatment is not without maternal or fetal risk. In about 10% of pregnant patients treated with intravenous labetalol or hydralazine, hypotension (defined as a drop in 30% of SBP) occurs⁵. Rapid and profound decrease in maternal blood pressure may result in hypoperfusion of the uterus secondary to a rightward shift occurring in the pressure autoregulation curve of the uterine arteries⁶, whereas a gradual decrease in blood pressure is safer for both the patient and the fetus, with less risk for maternal dizziness or fetal distress. When a non-reassuring fetal monitoring cannot be adequately resuscitated through maternal volume expansion, repositioning, or improvement in blood pressure, cesarean delivery is indicated.

In the antepartum or postpartum period, the most commonly prescribed oral agents for maintenance therapy include labetalol, methyldopa and Nifedipine. Scant guidelines exist on the introduction of a maintenance or long-acting agent anti-hypertensive medication to control blood pressure during an induction of labor. A recent randomized controlled trial compared oral nifedipine, labetalol and methyldopa in women with severe hypertension, with the primary outcome of non-severe blood pressure at 6 hours after administration of first dose, more common in patients assigned to Nifedipine⁷. In this study, the median time to delivery among all participants was 24 hours, with cesarean delivery for the indication of uncontrolled blood pressure occurring least frequently with Nifedipine (absolute difference of -5.2 compared to labetalol and -3.5 compared to methyldopa).

We propose a randomized double blind placebo controlled trial in women with preeclampsia with severe features undergoing induction of labor, to evaluate the efficacy of Nifedipine XL initiated in the intrapartum period on the need for acute therapy to reduce persistently severe range blood pressure.

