2.1 Rationale for a Randomized Controlled Trial

The lack of existing data on optimal hypertension management during induction of labor for preeclampsia with severe features leads to confusion among providers and significant variation in management. Exhausting the algorithms for intravenous labetalol and hydralazine, as well as oral immediate-release nifedipine, necessitates consideration of a continuous infusion of an anti-hypertensive agent, often requiring ICU-level care. Furthermore, intravenous therapy also introduces the risk for cesarean due to non-reassuring fetal status secondary to maternal hypotension. Therefore, patients with persistently severe range blood pressures are at risk for multiple intravenous or immediate-acting oral agents, as well as at risk for cesarean delivery to expedite treatment of preeclampsia.

To further describe best practice management of intrapartum preeclampsia with severe features, we aim to compare long-acting nifedipine 30mg to placebo. This dose will allow full range of options with intravenous labetalol or hydralazine, as well as immediate-release Nifedipine, for the treatment of hypertensive urgency.

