3.5 Population and Eligibility Criteria

a) Setting: This single center study will be conducted at The Ohio State University Wexner Medical Center.

b) Inclusion criteria:

1. Women aged 18-45 with a viable single or twin intrauterine pregnancy between 22 0/7 and 41 6/7 weeks gestation based on the best obstetric estimate by ACOG criteria.
2. Diagnosis of preeclampsia with severe features with decision made to induce labor. The patient may or may not have already received acute treatment for severe blood pressures.

c) Exclusion criteria:

- Known allergy or adverse reaction to Nifedipine or any medical condition where Nifedipine is contraindicated, such as galactose intolerance, severe GI stricture, and GI hypomotility disorder.
- Currently receiving Nifedipine XL as part of hypertension management prior to induction of labor
- Participation in another trial that affects the primary outcome without prior approval
- Physician/provider or patient refusal

- Participation in this trial in a prior pregnancy
- Triplet or higher order pregnancy

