4.2 Randomization and Baseline Visit Procedures

Randomization may occur upon confirmation that all inclusion/exclusion criteria are satisfied, after verification of participant consent and HIPAA authorization. Study staff will also verify participant contact information and obtain a Release of Information, as permitted by local policy, to collect outcome and serious adverse event (SAE) documentation. Patients will be assigned next sequential number and central pharmacy will dispense study drug or placebo depending on randomization allocation sequence.

Once the patient is randomized, the patient will receive a study drug or placebo from clinical nurse. She will be instructed to take 1 pill daily until delivery.

In addition to information collected for eligibility, gestational age, and EDC determination, the following information will be obtained at randomization from a patient interview followed by a review of her chart:

- Demographic information: age, race, insurance status
- Medical history: pre-pregnancy weight, current weight, height, chronic disease history
- Obstetrical history including outcomes of all prior pregnancies and which pregnancy(ies) was complicated by preeclampsia.
- Social history: marital status, years of education, alcohol use, tobacco use, and maternal drug use
- Record baseline blood pressure, and baseline preeclampsia laboratory data including platelets, creatinine, liver function tests and proteinuria status, if performed
- Medication use e.g. ASA prior to enrollment, antihypertensive medications including prior administration of acute antihypertensive medications, metformin, anti-platelet agents, etc

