6.0 Data Management

6.1 Data Collection Forms

Data will be collected on standardized forms on which nearly all responses have been pre-coded. Each form is briefly described below.

- Screening Log
- Eligibility Checklist
- Randomization: completed for all eligible women, lists randomized drug code number
- Baseline Form: includes detailed demographic and social data, medical & obstetrical history, and current pregnancy complications (to date), as applicable
- Study Drug lots: documents dispensing of study medication and the return of any unused study medication
- Maternal delivery and outcome forms: documents labor, delivery and postpartum information through the first 7 days after delivery
- Neonatal baseline form: records date and time of birth, delivery data and status at delivery for each fetus/infant
- Neonatal outcome form: records outcome data for all infants admitted to the NICU or special care nursery
- Patient status form: documents loss to follow-up/withdrawal status, side effects since the last dose
- Will do an intrapartum BP log.

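### Section 3.3 words the relative limb of maternal hypotension as a pressure below 30% of baseline, not a 30% decrease; on SBP or MAP, at baselines up to 216 mmHg, it adds no case to MAP <65 mmHg

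*Combined protocol and SAP*

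**What the plan says.** Section 1.4 lists "maternal hypotension and other adverse events" among the secondary aims without defining hypotension. The only scoring rule is in Section 3.3: "Maternal hypotension (<30% baseline or mean arterial pressure" below 65 mmHg. The rule has two limbs, a relative one and an absolute one. The relative limb does not mention a fall and does not name systolic, diastolic or mean pressure.

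No other section restates or corrects the rule. The statistical analysis plan (headed 2.6, after Section 5.0) does not mention hypotension. Section 2.0, describing a cited study of intravenous treatment, says "hypotension (defined as a drop in 30% of SBP) occurs" in about 10% of patients. Section 4.2 has staff "Record baseline blood pressure, and baseline preeclampsia laboratory data" at randomization, and Section 6.1 adds "Will do an intrapartum BP log", so the readings needed to score either limb are to be collected.

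**The concern.** A relative limb normally catches large falls in women who start from a high pressure and so remain above an absolute floor. Women in this trial are likely to start high: the diagnostic thresholds in Section 3.1 are 160/110 and 140/90. If the relative limb is followed as written, it cannot do that job, and the outcome reduces to MAP below 65 mmHg.

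Maternal hypotension is a named safety outcome in a placebo-controlled trial of an added antihypertensive. The rationale in Section 2.1 also gives it weight, noting that "intravenous therapy also introduces the risk for cesarean due to non-reassuring fetal status secondary to maternal hypotension". At stake is whether large falls that stop short of MAP 65 appear in the reported count. They would go uncounted in both arms; the documents give no basis for saying how the comparison between arms would change.

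**Working it through.** The plan gives no rate, power or expected count for hypotension, so there is no figure to reproduce. The check is threshold arithmetic.

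**Inputs.** Relative limb as written: below 30% of baseline (Section 3.3). Absolute limb: MAP <65 mmHg (Section 3.3). MAP = (SBP + 2 × DBP)/3. Individual baselines are assumptions, because the documents give none; 160/110 and 140/90 are the diagnostic thresholds in Section 3.1, and 150/100 lies between them.

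**1. The literal limb on SBP.** Cut-off = 0.30 × baseline SBP.
- From 160: 0.30 × 160 = 48 mmHg. From 140: 0.30 × 140 = 42 mmHg.
- MAP cannot exceed SBP. At baseline 216, 0.30 × 216 = 64.8, which is below 65, so every qualifying reading has MAP <65.
- An enumeration over integer baseline SBP 120 to 216 and integer readings (SBP ≥20, DBP from 5 up to SBP) found 95,947 baseline and reading combinations that meet the limb. None has MAP ≥65.
- The limit is 65/0.30 = 216.7. Above it an exception is possible only with a very narrow pulse pressure: from 240 the cut-off is 72, and a reading of 71/62 has MAP (71 + 124)/3 = 65.0.

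**2. The literal limb on MAP.** From 160/110, baseline MAP is (160 + 220)/3 = 126.7 and the cut-off is 38.0. From 140/90, baseline MAP is 106.7 and the cut-off is 32.0. Both lie well inside MAP <65, as does any cut-off from a baseline MAP up to 216.

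**3. The literal limb on DBP.** This is the one component on which it could add a case. From DBP 110 the cut-off is 33. At DBP 32, MAP ≥65 needs SBP ≥ 195 − 64 = 131, a reading of 131/32 with a pulse pressure of 99 mmHg.

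**4. What is left out if the limb is followed as written.** Each reading below is a fall of at least 30% in SBP with MAP still above 65.

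| Assumed baseline | Reading | Fall in SBP | MAP of reading |
|---|---|---|---|
| 160/110 | 108/62 | 1 − 108/160 = 32.5% | (108 + 124)/3 = 77.3 |
| 150/100 | 104/60 | 1 − 104/150 = 30.7% | (104 + 120)/3 = 74.7 |
| 140/90 | 97/56 | 1 − 97/140 = 30.7% | (97 + 112)/3 = 69.7 |

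**5. How far pressure must fall before the absolute limb counts it.** If SBP and DBP fall in the same proportion, the fall needed is 1 − 65/baseline MAP: 48.7% from 160/110, 44.3% from 150/100 and 39.1% from 140/90. All three are well beyond 30%.

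**6. Why the component must be named even if a decrease is inferred.** From 160/110, a reading of 110/82 is a 31.3% fall in SBP, but its MAP of 91.3 is a fall of 27.9%. A reading of 120/70 is a 25.0% fall in SBP, but its MAP of 86.7 is a fall of 31.6%. Each is a case on one component and not on the other, and neither has MAP <65.

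**The case against.** The strongest reply is that nobody would score the outcome literally. SBP below 48 mmHg is not a credible definition of maternal hypotension, and placed beside MAP <65 the phrase reads as shorthand for 30% below baseline. Section 2.0 uses 30% in that sense. If scorers read it that way, the gap in step 4 is zero. Most of this stands, and it is why the point is minor. It does not remove the point, because this is the trial's only stated rule for the outcome and it undercounts if followed. Inferring a decrease also leaves step 6 open.

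A reader might infer more than the documents support:
- *That the protocol holds two conflicting definitions of hypotension.* It does not. The 30% drop in Section 2.0 belongs to a cited study; it is evidence of intent, not a second trial definition.
- *That Section 2.0 sets out any 30% fall as the trial's own concern.* The sentence "Rapid and profound decrease in maternal blood pressure may result in hypoperfusion of the uterus" is cited background about falls that are fast and deep, and the text contrasts them with gradual ones. It gives little support to a 30% rule.
- *That the literal limb can never add a case.* Steps 1 and 3 show exceptions, at baseline SBP above 216.7 and on DBP with extreme pulse pressures.
- *That the gap vanishes once baseline MAP is below 65/0.70 = 92.9.* This holds on MAP or for proportional falls only. On SBP, an assumed 120/75 (MAP 90.0) falling to 82/58 is a 31.7% drop with MAP 66.0.

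**Conclusion.** The relative limb is wrong as written, and the point is minor. On SBP or MAP, for baselines up to 216 mmHg, it adds no case to MAP <65, so falls of 30% or more with MAP at 65 or above are not counted if the rule is applied as it stands.

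This rests on the literal reading being used; under the probable intent nothing is lost. The example pressures are assumed, and the number of women affected cannot be estimated from the documents. A symbol altered in text conversion cannot be excluded, so the sign should be confirmed against the source file; the missing component would remain either way.

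A reader might conclude that the trial will under-report hypotension or that its safety assessment is compromised. The documents do not support this: they do not show how the outcome will in fact be scored, and only one secondary outcome is involved. The primary outcome and the sample size are unaffected.

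**What to change.** For outcome scoring, reword the limb in Section 3.3 as a decrease of at least 30% from the baseline blood pressure recorded at randomization (Section 4.2), or MAP <65 mmHg. In the same line, state which pressure component the 30% applies to; that choice is for the investigators, and SBP would match the cited study in Section 2.0. Adding the word decrease after the existing sign is not enough, because less than a 30% decrease reverses the meaning; the operator must change too.

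In settling the reference reading, the investigators should note that Section 3.5 states "The patient may or may not have already received acute treatment for severe blood pressures", so a baseline taken after such treatment may give a lower reference.

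The cost is one line of text. Baseline pressure and the intrapartum log are already in the data collection plan, and Section 3.0 already specifies analysis by intent to treat. The documents do not give the trial's status; if the outcome has already been scored, the report should state the rule that was used.

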3.0 Study Design

This is a randomized double blind placebo controlled trial comparing Nifedipine 30mg XL to placebo in 110 patients after decision has been made to proceed with induction of labor for the diagnosis of preeclampsia with severe features.

Potential study participants will be identified at the time of admission to the labor & delivery unit. Eligibility criteria will be verified. At the time of enrollment, patients will be randomized to either the study drug (oral Nifedipine XL 30mg) or identical placebo. Participants will receive the first dose of the study medication after enrollment unless recorded blood pressure is <120/70. Dosing will continue every 24 hours through delivery. Algorithms for the administration of intravenous labetalol or hydralazine will be utilized by the primary provider at his or her discretion. Postpartum management of hypertension with oral medications will be unblinded and at the provider's discretion.

This study is a randomized, double-blind, placebo controlled single center clinical trial conducted at The Ohio State University Wexner Medical Center, where approximately 216 women are delivered for preeclampsia with severe features each year. These women will be randomized at the time of induction of labor into two groups.

- Oral administration of 30mg Nifedipine XL q24 hours until delivery
- Matching placebo group q24hrs until delivery
- Women may take the study drug/placebo concurrently with intravenous labetalol or hydralazine or immediate release Nifedipine for the treatment of severe blood pressures during cervical ripening and/or induction of labor per unit protocol.
- All other obstetric care will be at the discretion of the primary provider, including but not limited to cervical ripening and augmentation methods, intrapartum resuscitation, IV magnesium for seizure prophylaxis and recommendations regarding mode of delivery. Data will be collected on these components of routine obstetric care. Analysis will be by intent to treat.

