3.4 Study Groups

This study is a randomized, double-blinded placebo controlled single center clinical trial conducted at OSU Wexner Medical Center of 110 women with diagnosis of preeclampsia with severe features. These women will be randomized at the time of admission to the labor & delivery unit to one of two groups:

- Daily Nifedipine 30mg XL
- Identical appearing placebo

Participants in the study will have the study medication administered by their nurse at time of enrollment and randomization, and every 24 hours thereafter until delivery. All other obstetric care will be at the discretion of the primary provider, including but not limited to: treatment of hypertensive urgency, timing and mode of delivery. Data will be collected on these components of routine obstetric care.

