5.0 Sample Size and Power

For the purposes of sample size estimation, it is assumed that 85% of women with diagnosis of preeclampsia with severe features receive acute IV antihypertensive therapy and 74% will require additional IV hypertensive therapy throughout induction of labor process. Assuming rate of additional acute IV antihypertensive (primary outcome) without use of maintenance long acting antihypertensive therapy is 74%. It is estimated that sample size of 110 women is required to demonstrate at least a 40% reduction in use of additional acute antihypertensive therapy with the use of nifedipine 30XL (from 74% to 44%), with a power of 80%, and type I error of 5% 2-sided.

Primary Outcome		Treatment Effect	Power	Total N
Placebo	Nifedipine			
75%	52.5%	30% reduction	80%	140
			85%	160
			90%	188
	45%	40% reduction	80%	82
			85%	92
			90%	108
70%	49%	30% reduction	80%	170
			85%	194
			90%	226
	42%	40% reduction	80%	97
			85%	110
			90%	128
65%	45.5%	30% reduction	80%	202
			85%	230
			90%	270
	39%	40% reduction	80%	114
			85%	130
			90%	150

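### The adverse maternal composite contains two durations with no cut-off and a treatment-exposure item, so it cannot be scored as an any-event harm outcome as written

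*Combined protocol and SAP*

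**What the plan says.** Section 1.4 names, among the secondary aims, "maternal hypotension and other adverse events, and a composite of maternal and perinatal adverse outcomes", without components or a scoring rule. Section 3.3 supplies the maternal components in a single bracket. It begins "Composite of adverse maternal outcomes (time duration to need for acute antihypertensive therapy, receipt of second dose study drug, time from randomization to delivery" and runs on through 12 clinical events, from seizure to maternal death.

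The same list gives another duration, "Time from enrollment to hospital discharge", a bullet of its own outside any composite.

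On dosing, section 3.0 says "Dosing will continue every 24 hours through delivery", and section 3.4 has the study medication given at enrollment and "every 24 hours thereafter until delivery".

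Section 3.2 sets the primary outcome: "The primary aim is the need for intravenous or immediate-release oral therapy for acute treatment of severe hypertension".

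Section 2.6 (Statistical Analysis Plan) provides methods for rates and proportions for the many secondary endpoints that are dichotomous, and unspecified standard methods for continuous variables. It does not mention the composite.

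**The concern.** There are two separate faults in one secondary outcome.

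- **Two items cannot be scored.** Time to need for acute therapy and time from randomization to delivery have no cut-off. Every woman has a time to delivery, so without a threshold that item is neither present nor absent. The plan gives no cut-off, ranking, weighting or time-to-event rule for a composite that mixes durations with events.
- **One item is not harm.** Receipt of a second dose is yes/no, but under the 24-hourly schedule it mainly records that the woman had not yet delivered at about 24 hours.

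The composite is one of the few planned summaries of maternal harm, and the open scoring choices do not all push the same way. Turning the first duration into receipt of acute therapy would put the primary outcome inside the harm composite, so the hoped-for efficacy effect would appear as fewer adverse outcomes even with equal harm. Keeping second-dose receipt would dilute a real harm difference if its rate were equal in the arms, and would carry a difference in time to delivery into the harm result if it were not.

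**Working it through.** **Component count (section 3.3).** 15 items = 2 durations without a threshold + 1 exposure item + 12 clinical events. Comparison as any event versus none is the natural reading of such a composite, but it is not stated.

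**No figure to reproduce.** The documents give no event rate or power for the composite. What follows shows only how far the scoring choice can move the result.

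**Inputs**
- 110 women at 1:1, so 55 per arm; two-sided 5% (sections 3.7 and 5.0).
- Acute therapy 74% on placebo and 44% on nifedipine. Section 5.0 says "Assuming rate of additional acute IV antihypertensive (primary outcome) without use of maintenance long acting antihypertensive therapy is 74" percent. This is a proxy, because section 5.0 refers to additional IV therapy while section 3.2 also counts immediate-release oral therapy.
- Second-dose rate: not given. The one anchor is the cited oral-antihypertensive trial (section 2.0), in which "the median time to delivery among all participants was 24 hours". That suggests about 50%; because the population differs, 30-60% is shown.
- Harm rates (any of the 12 events): assumed.

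**Formulas.** With independent components, composite = 1 − (1 − a)(1 − h), where h is the harm rate and a the rate of the added item. With p̄ the mean of the two composite proportions,

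power = Φ{[|p₁ − p₂| − 1.96√(2p̄(1 − p̄)/55)] / √([p₁(1 − p₁) + p₂(1 − p₂)]/55)}.

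**1. First duration read as received acute therapy; equal harm in both arms**

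| Harm h | Placebo | Nifedipine | Chance of a significant difference |
|---|---|---|---|
| 10% | 1 − 0.26×0.90 = 76.6% | 1 − 0.56×0.90 = 49.6% | 85% |
| 20% | 1 − 0.26×0.80 = 79.2% | 1 − 0.56×0.80 = 55.2% | 77% |
| 40% | 1 − 0.26×0.60 = 84.4% | 1 − 0.56×0.60 = 66.4% | 59% |

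If harm clusters with acute therapy (odds ratio 2 to 5, margins fixed), the chance is 85-87% at 10% harm and 61-65% at 40%, so the independence assumption does not drive the result.

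**2. Second dose kept in, same rate in both arms; true harm 30% vs 10%**

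On the 12 events alone, power is 75%. With the second-dose item added:

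| Association with harm | 30% get a second dose | 50% | 60% |
|---|---|---|---|
| Independent | 31% (51% vs 37%) | 19% (65% vs 55%) | 14% (72% vs 64%) |
| Odds ratio 2 | 25% | 13% | 10% |
| Odds ratio 3 | 22% | 11% | 8% |
| Odds ratio 0.2 | 45% | 37% | 32% |
| Never coincide | 56% | 63% | 75% |

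From a smaller harm difference, 20% vs 10%, power is 31% on the 12 events alone and 8% with an independent 50% second-dose rate (60% vs 55%).

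**3. Unequal second-dose rates (50% vs 30%, assumed), equal harm of 20%**

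1 − 0.50×0.80 = 60% against 1 − 0.70×0.80 = 44%. The chance of a significant difference is 39%, with no difference in harm.

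**The case against.** The strongest reply is that this is a drafting slip. The three items come first, ahead of an unbroken run of clinical events, and a similar duration has its own bullet in the same section. Once moved out of the bracket, the durations would fall under section 2.6's provision for continuous variables. This is plausible, but the text does not say it, and an analyst following the protocol would have to guess. The correction is the same either way.

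It is also true that the plan never says the composite will be scored as any event versus none. That narrows the claim without removing it: no other rule is given, so the composite is undefined under every reading.

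The illustrations are fairly criticised as resting on assumptions. Nothing in the text proposes recoding the first duration as receipt of therapy. The 30% vs 10% case starts from favourable power, and the unequal second-dose rates have no source. A negative association is plausible, since a serious event could hasten delivery before a second dose, and it softens the dilution; even so, an odds ratio of 0.2 leaves power at 32-45%. If the two never coincided, power would be 56-75%, so the loss would range from none to 19 points. These points limit the figures. They do not touch the definitional fault.

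**Conclusion.** The concern holds, and the composite is wrong as written. Following the list literally counts a treatment-exposure item as an adverse outcome and includes two items that cannot be present or absent; no section resolves this. That conclusion rests on the text alone.

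The size depends on assumed harm and second-dose rates, on 74% and 44% as a proxy for acute-therapy rates, and on 55 women per arm. Within those assumptions the scoring choice could produce an apparent safety benefit with 59-85% probability under independence, or remove most of the power to detect a real harm difference. The point should be fixed, but it concerns one secondary outcome; the primary outcome, sample size and primary analysis are unaffected.

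**What to change.** Before unblinding, amend section 3.3 and the analysis plan as follows.

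- Take the three items out of the maternal composite and score it as any versus none of the 12 clinical events: seizure; stroke or cortical blindness; pulmonary edema; oliguria; DIC; ICU admission; dialysis; mechanical ventilation; abruption; postpartum hemorrhage; transfusion of blood products; maternal death. Tabulate each by arm.
- State in advance how oliguria and postpartum hemorrhage are defined. The documents do not say, and part of the scoring would otherwise stay open.
- Report time from randomization to delivery, second-dose receipt and time to first acute therapy as separate secondary or exposure variables. For the last, use a time-to-event method that keeps women who never needed acute therapy in the analysis.

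The cost is wording only; no data are needed beyond what the listed items already require. The downside is a lower composite event rate and limited power at 110 women, so report the composite mainly as a difference with a confidence interval. The 95% half-width is 1.96√(2p(1 − p)/55): about 11 percentage points at p = 10% in both arms and 15 at p = 20%.

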2.6 Statistical Analysis Plan

Standard comparisons of characteristics between groups will be conducted at baseline. It

is anticipated that the randomization scheme will balance the groups for these covariates and they will not be adjusted for in the primary analysis.

The primary analysis will compare incidence of the outcome between the 2 study groups. If the two groups show a difference in the incidence of the primary outcome, interactions will be evaluated and subgroup analyses conducted to determine whether the effect prevails.

Lost to follow up should not occur given study design and no follow up is scheduled. Since many of the secondary endpoints are dichotomous variables like the primary outcome, standard statistical methods for rates and proportions will be appropriate. Continuous variables will be compared using standard statistical methods,

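### If scored as any component, the neonatal composite largely measures NICU admission, because serious events in a NICU infant cannot change that infant's score; a version without NICU admission should be added

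*Combined protocol and SAP*

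**What the plan says.** Section 3.3 defines one neonatal outcome, a composite. The list opens with "Composite of adverse neonatal outcomes (intrapartum fetal demise, abruption, neonatal death" and closes with "Apgar score <7 at 5 minutes, intubation, convulsions, IVH, confirmed sepsis, RDS requiring O2, NICU admission". The components carry no ranking or weights, and no neonatal component appears as a separate secondary outcome.

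Section 6.1 gives one-line descriptions of the forms. Three of them matter here:

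- Every infant: "Neonatal baseline form: records date and time of birth, delivery data and status at delivery for each fetus/infant".
- Admitted infants: "Neonatal outcome form: records outcome data for all infants admitted to the NICU or special care nursery".
- Mothers: "Maternal delivery and outcome forms: documents labor, delivery and postpartum information through the first 7 days after delivery".

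The scoring rule for the composite is not given. The closest text is in the Statistical Analysis Plan section (numbered 2.6, after section 5.0): "Since many of the secondary endpoints are dichotomous variables like the primary outcome", standard methods for proportions will be used. Section 3.5 admits singleton and twin pregnancies "between 22 0/7 and 41 6/7 weeks gestation". No NICU admission rate or neonatal event rate is given anywhere.

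**The concern.** The component that triggers the neonatal outcome form is itself enough to make the composite positive. For a NICU infant, therefore, the information on that form adds nothing to the score. For an infant never admitted, the form is not described as being completed, so later serious events have no stated neonatal form.

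The composite may then be little more than NICU admission plus whatever is visible at birth. Eligibility spans very preterm to post-term gestations, so admission may be common and may depend a good deal on gestational age at enrolment, although the documents give no figure for either. Section 1.4 lists perinatal adverse outcomes among the secondary aims, and this composite is the only neonatal outcome in section 3.3. A trial that reports it alone could show similar arms while serious morbidity differed among the admitted infants.

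**Working it through.** The plan has no figure to reproduce on this point. The check sets sections 3.3 and 6.1 side by side and then uses arithmetic on assumed rates.

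**Step 1: what each group of infants can contribute, under an any-component score.**

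| Infant | Forms described | Can the outcome form change the score? |
|---|---|---|
| NICU | baseline and outcome | No, already positive |
| Special care only, if not counted as NICU | baseline and outcome | Yes |
| Never admitted | baseline only | No such form; only birth events are visible |

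The baseline form can plausibly hold intrapartum demise, Apgar score, delivery-room intubation and delivery-room death. The maternal form can plausibly hold abruption.

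**Step 2: the composite as a formula.**

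P(composite) = P(NICU) + P(not NICU and at least one other recorded component).

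The serious-event rate among NICU infants does not enter. Assume NICU rates of 30%, 50% and 70%, and vary serious events among NICU infants from 10% to 60%:

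- With no special-care-only infants, NICU admission and the outcome form together supply exactly 30%, 50% and 70%, whatever the serious-event rate.
- If 10% of infants go to special care only and 10% of those have an event, this adds 0.10 × 0.10 = 1 point, giving 31%, 51% and 71%.
- If 1% of never-admitted infants have an event, this is 0.01 × (1 − 0.70 − 0.10) = 0.2 points at the low end and 0.01 × (1 − 0.30) = 0.7 points at the high end. The outcome form would not record these.

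**Step 3: what could be hidden.** Assume 50% NICU admission in each arm, with all serious morbidity inside it. If serious morbidity rises from 10% to 25% or 30% of infants, the composite difference is 50% − 50% = 0. This zero follows from the assumptions of equal admission and full nesting. If instead a share f of the extra events fell in infants who would otherwise have scored negative and are now recorded as positive, the composite would move by f × 15 points in the 10% against 25% case: 0 at f = 0, 5 points at f = 1/3, and 15 points at f = 1.

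**Step 4: power if the same events were scored without NICU admission.** Inputs: 55 per arm (110/2, sections 3.0 and 5.0), two-sided 5%, one infant per woman, arcsine approximation:

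h = 2[asin(√p₂) − asin(√p₁)], power ≈ Φ(h√(n/2) − 1.96), with √(55/2) = 5.244.

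| Serious morbidity | h | h√(n/2) | Power |
|---|---|---|---|
| 10% vs 15% | 0.152 | 0.797 | about 12% |
| 10% vs 20% | 0.284 | 1.488 | about 32% |
| 10% vs 25% | 0.404 | 2.117 | about 56% |
| 10% vs 30% | 0.516 | 2.705 | about 77% |

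The added composite can therefore detect only large differences, but it does respond to them. The listed composite does not respond to differences that lie wholly within admitted infants.

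**The case against.** The strongest reply has four parts.

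- **Scoring.** The any-component rule is inferred. A count or a ranked score would remove the masking. This stands as a condition on the point, and is a reason to state the rule.
- **The zero difference is assumed.** Real fetal compromise might also lead to new admissions or low Apgar scores, and the composite would then move. This stands. The claim is limited to morbidity among infants who would be admitted in either case.
- **Little is lost.** The form is completed for admitted infants, so their components could be tabulated without redesign. True, but the plan does not commit to it.
- **Other sources.** Section 4.2 provides a release of information for outcome and serious adverse event documentation. It does not name infants, so it answers the gap only in part. The form descriptions in section 6.1 are brief, list no fields, and do not expressly exclude other infants.

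A reader might also infer stronger things that the documents do not support. One is that every component is missing for infants never admitted, or that a delivery-room death would go unrecorded. The baseline form covers status at delivery for every infant, and a low 5-minute Apgar would very probably make such an infant positive anyway. Another is that the Background (section 2.0) identifies a fall in maternal pressure from the study drug as the main fetal danger. That section ties hypoperfusion to acute treatment with a rapid fall, and describes a gradual reduction as safer. A third is that gestational age would bias the comparison. Randomization makes it a source of noise, not of bias.

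**Conclusion.** The point holds in a limited form. Under an any-component yes/no score, serious events in NICU infants cannot change their score, and the composite largely measures NICU admission plus events visible at birth. A difference in serious morbidity confined to infants admitted in either arm would appear as zero, at any admission rate. Later events in infants never admitted lack a stated neonatal form, but they are probably few: 0.2 to 0.7 points if 1% of them have one. Masking within the NICU is the larger issue.

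The conclusion rests on the inferred scoring rule and on brief form descriptions, and every rate used is an assumption. It concerns one secondary outcome and leaves the primary outcome and the sample size untouched. It is worth correcting because the change is cheap and this is the only neonatal outcome in section 3.3.

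**What to change.** In section 3.3, keep the listed composite and state that it is positive if any component occurs. Add, as a prespecified secondary comparison, the same composite without NICU admission, and commit to tabulating each component by arm.

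In section 6.1, require the listed neonatal components to be recorded for every liveborn infant to hospital discharge or death, with non-admission as a recorded answer instead of a reason to omit the form.

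The cost is wording in two sections and a short chart abstraction for non-admitted infants at one centre, at most about 110 births plus co-twins. The added composite will be rarer, with a wider interval on the relative scale and only about 32% power for 10% against 20%. It should be presented as an estimate with its confidence interval, and a non-significant result should not be read as evidence of safety. Removing NICU admission from the composite altogether is a debatable trade-off and is not needed.
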